5.2.2.2.3 Relative decline from baseline in FVC % pred at 52 weeks

Patients will be categorised based on the relative decline from baseline in FVC % pred greater than 5% or greater than 10% at week 52. The categorisations will be handled as separate endpoints, and the proportion of patients with a decline of greater than 5% as well as the proportion of patients with a decline of greater than 10% will be evaluated separately between the two treatment groups. Please note that patients who fulfil the criterion of a relative decline of greater than 10% also automatically fulfil the criterion of a relative decline of greater than 5%, and will therefore be counted in both endpoint evaluations. Specific rules of handling of missing items are detailed in [Section 6.6.2.3](#).

5.2.2.2.4 Change from baseline in Living with Pulmonary Fibrosis Symptoms and Impact Questionnaire (L-PF) Dyspnea and Cough Domain Scores at week 52

The Living with Pulmonary Fibrosis (L-PF) questionnaire is a 44 item questionnaire with two modules: 1) symptoms (23 items) and 2) impacts (21 items). L-PF was developed with the input of patients with pulmonary fibrosis (PF) and thus is intended to capture perceptions specific to PF patients. The Symptoms module yields three domain scores: 1) dyspnea, 2) cough and 3) fatigue as well as a total Symptoms score. The Impacts module yields a single Impacts score. Symptoms and Impacts scores are summed to yield a total L-PF score. Scoring is performed as a summary score, the mean of the dimension ratings multiplied by 100. Summary score range from 0-100, the higher the score the greater the impairment.

The absolute change from baseline in the L-PF symptoms dyspnea domain score at week 52 as well as the absolute change from baseline in the L-PF symptoms cough domain score at week 52 will be computed and evaluated separately. Scoring instructions for L-PF are described in [Section 9.2](#). Specific rules of handling of missing items are detailed in [Section 6.6.2.1.2](#).

5.3 FURTHER ENDPOINTS

This section includes endpoints over 52 weeks (Part A) as well as further endpoints over the whole trial (Part A and Part B).

5.3.1 Endpoints over 52 weeks

Please note: Additional information about the 52 weeks analysis period can be found in [Section 6.1.1](#), according to the type of endpoint.

5.3.1.1 Time to first non-elective hospitalisation or death over 52 weeks

Time to non-elective hospitalization assessment will be based on the date of hospitalization collected on a specific hospitalization eCRF page. The eCRF page will capture whether the non-elective hospitalization was due to respiratory cause, and the primary admission diagnosis according to the investigator. Cause of non-elective hospitalizations will not be adjudicated by the AC.

For those patients who either experience a non-elective hospitalisation or who die due to any cause within the first 52 weeks, time to first non-elective hospitalisation or death [days] will be computed as:

- Earliest of date of first non-elective hospitalisation or death – date of first drug intake + 1

Patients who did not experience any event within the first 52 weeks will be censored according to the mechanism for censoring as described in Table 5.3.1.1: 1.

Table 5.3.1.1: 1 Censoring Rules for Time to first non-elective hospitalisation or death over 52 weeks

Rule #	Situation	Outcome (event or censored)	Date of event or censoring
1	Patient had a documented non-elective hospitalisation or died within the first 52 weeks and the date of the event is known	Event	Earliest Date of event
2	Patient had a documented non-elective hospitalisation or died within the first 52 weeks and the date of the event is unknown	Event	Imputed date of event
3	Patient did not have a documented non-elective hospitalisation and is alive after 52 weeks	Censored	Day 373 (372 days after first drug intake)
4	Patient status is unknown	Censored	Date of last contact when the patient was known to be alive and event free

5.3.1.2 Absolute change from baseline in FVC at week 52

The absolute change from baseline in FVC at week 52 will be computed and shown. The evaluation will be done by assessing the absolute change in FVC in ml between week 52 and baseline; and in addition to that, by assessing the absolute change from baseline in FVC in % pred between week 52 and baseline. The changes in these two parameters between the two treatment groups will be depicted and described.

Specific rules of handling of missing items are detailed in [Section 6.6.2.1](#).

5.3.1.3 Absolute decline from baseline in FVC % pred at week 52

Patients will be categorised based on the absolute decline from baseline in FVC % pred greater than 5% or greater than 10% at week 52. The categorisations will be handled as separate endpoints, and the proportion of patients with a decline of greater than 5% as well as the proportion of patients with a decline of greater than 10% will be evaluated separately between the two treatment groups. Please note that patients who fulfil the criterion of an absolute decline of greater than 10% also automatically fulfil the criterion of an absolute decline of greater than 5%, and will therefore be counted in both endpoint evaluations. Specific rules of handling of missing items are detailed in [Section 6.6.2.3](#).

5.3.1.4 Absolute change from baseline in Carbon Monoxide Diffusion Capacity (DLCO) % pred over 52 weeks

Single-breath DLCO measurements will be carried out according to the American Thoracic Society (ATS) / European Respiratory Society (ERS) guideline on DLCO measurements ([13](#)) DLCO and the corresponding alveolar volume will be measured at time points given in the Flowcharts in the CTP.

DLCO values will be adjusted for altitude, carboxyhaemoglobin (COHb) and the most recent haemoglobin value. For predicted normal values of DLCO, different sites may use different prediction formulas, based on the method used to measure DLCO. In any case, the calculation method used must be in compliance with the ATS/ERS guideline on DLCO measurements and the prediction formula appropriate for that method.

For analyses DLCO % pred at week 52 will be computed as follows:

- $(\text{mean DLCO}) / (\text{DLCO predicted}) \times 100\%$,

where mean DLCO is the mean of the two valid measurements entered in the eCRF (in case only one valid measurement then this one will be used) and

- DLCO predicted (men) = $(11.114 \times \text{height [m]}) - (0.066 \times \text{age [years]}) - 6.03$
- DLCO predicted (women) = $(8.176 \times \text{height [m]}) - (0.049 \times \text{age [years]}) - 2.746$

The value of DLCO % pred will always be presented after correction for Haemoglobin. Percent predicted DLCO corrected for haemoglobin (Hb) expressed in g/dL ([13](#)) can be calculated as:

- For men:

$$\text{Percent predicted DLCO corrected for Hb} = \frac{\text{Percent predicted DLCO} \times (10.22 + Hb)}{1.7Hb}$$

- For women:

$$\text{Percent predicted DLCO corrected for Hb} = \frac{\text{Percent predicted DLCO} \times (9.38 + Hb)}{1.7Hb}$$

Please note that different units for DLCO are dealt with the following way:

- If unit of DLCO measured value is given as “mmol/min/kPa”, then the value of DLCO is used for the computations
- If unit of DLCO measured value is given as “ml/min/mmHg”, then the value of DLCO is divided by 2.987 before it is used in the computations

The absolute change from baseline in DLCO % pred at week 52 will be depicted and compared between the two treatment groups.

5.3.1.5 Living with Pulmonary Fibrosis Symptoms and Impact Questionnaire (L-PF)

A more detailed description of the L-PF can be found in [Section 5.2.2.2.4](#) or in the CTP.

The absolute change from baseline in the L-PF total score, the L-PF impact score, the L-PF symptoms total score and the L-PF symptoms fatigue domain score all at week 52 will be computed and evaluated. Scoring instructions for L-PF are described in [Section 9.2](#). Specific rules of handling of missing items are detailed in [Section 6.6.2.1.2](#).

5.3.1.6 Change from baseline in Pulmonary Fibrosis Impact on Quality of Life Scale (PF-IQOLS) summary score at week 52

The PF-IQOLS scale was developed to measure the impact of a disease and its treatment on the patient's quality of life. The IQOLS includes 16 dimensions and a 5-point standard Likert-type response scale on which patients rate the impact of the disease on their quality of life ([14](#), [15](#)). Scoring of IQOLS is performed as a summary score, the average of the individual dimension ratings. Summary scores range from 1.0-5.0 with greater scores reflecting a worse quality of life.

The absolute change from baseline in the PF-IQOLS summary score at week 52 will be computed and evaluated between the two treatment groups. Scoring instructions for PF-IQOLS are described in [Section 9.3](#). Specific rules of handling of missing items are detailed in [Section 6.6.2.1.3](#).

5.3.2 Endpoints over the whole trial

Part B of the trial (a variable treatment period beyond 52 weeks on patient level) will start after Part A has concluded, and is conducted in order to collect supportive longer term data on the effect of nintedanib in patients with PF-ILD in a controlled manner, especially for the early enrollers. Due to the varying length of follow-up in Part B of the trial, the efficacy measures incorporating data from Part A and Part B will focus on time-to-event endpoints.

5.3.2.1 Time to death over the whole trial

Date of death for an individual patient will be obtained from either the AE reporting page for patients with AEs leading to death or the information from the vital status assessment page. The start date of time at risk is the date of first drug intake, and, in general, patients who did not die during the trial will be censored at the last known date when the patient was alive.

For patients with known date of death (regardless of the cause of death) at any point within the trial, the derivation will be as follows:

- Time to death = Date of death – date of first drug intake + 1

Patients who did not experience any event during their trial participation will be censored according to the mechanism for censoring as described in Table 5.3.2.1: 1.

Table 5.3.2.1: 1 Censoring Rules for Time to death over the whole trial

Rule #	Situation	Outcome (event or censored)	Date of event or censoring
1	Patient died and date of Death is known	Event	Date of event
2	Patient died and date of Death is unknown	Event	Imputed date of event
3	Patient is alive	Censored	Date of last contact when the patient was known to be alive
4	Patient status is unknown	Censored	Date of last contact when the patient was known to be alive

5.3.2.2 Time to first acute ILD exacerbation or death over the whole trial

For those patients who either experience acute ILD exacerbations or who die due to any cause at any point in the study, time to first acute ILD exacerbation or death [days] will be computed as:

- Earliest of date of first documented acute ILD exacerbation or death – date of first drug intake + 1

Patients who did not experience any event during their trial participation will be censored according to the mechanism for censoring as described in [Table 5.3.2.2: 1](#).

Table 5.3.2.2: 1 Censoring Rules for Time to first acute ILD exacerbation or death over the whole trial

Rule #	Situation	Outcome (event or censored)	Date of event or censoring
1	Patient had a documented acute ILD exacerbation or died and the date of the event is known	Event	Earliest Date of event
2	Patient had a documented acute ILD exacerbation or died and the date of the event is unknown	Event	Imputed date of event
3	Patient did not have a documented acute ILD exacerbation and is alive	Censored	Date of last contact when the patient was known to be alive and event free
4	Patient status is unknown	Censored	Date of last contact when the patient was known to be alive and event free

5.3.2.3 Time to first non-elective hospitalisation or death over the whole trial

Time to non-elective hospitalization assessment will be based on the date of hospitalization collected on a specific hospitalization eCRF page.

For those patients who either experience a non-elective hospitalisation or die due to any cause within the trial, time to first non-elective hospitalisation or death [days] will be computed as:

- Earliest of date of first non-elective hospitalisation or death – date of first drug intake + 1

Patients who did not experience any event during their trial participation will be censored according to the mechanism for censoring as described in [Table 5.3.2.3: 1](#).

Table 5.3.2.3: 1 Censoring Rules for Time to first non-elective hospitalisation or death over the whole trial

Rule #	Situation	Outcome (event or censored)	Date of event or censoring
1	Patient had a documented non-elective hospitalisation or died and the date of the event is known	Event	Earliest Date of event
2	Patient had a documented non-elective hospitalisation or died and the date of the event is unknown	Event	Imputed date of event
3	Patient did not have a documented non-elective hospitalisation and is alive	Censored	Date of last contact when the patient was known to be alive and event free
4	Patient status is unknown	Censored	Date of last contact when the patient was known to be alive and event free

5.3.2.4 Time to death due to respiratory cause over the whole trial

Analysis of time to death due to respiratory cause will be based on the adjudicated cause of death as determined by an independent Adjudication Committee (AC). For those patients who died, and whose death is attributed by the AC to respiratory causes at any time within the trial, time to death due to respiratory cause [days] will be computed as:

- Date of death – date of first drug intake + 1

Patients who did not experience any event during their trial participation will be censored according to the mechanism for censoring as described in Table 5.3.2.4: 1.

Table 5.3.2.4: 1 Censoring Rules for Time to death due to respiratory cause over the whole trial

Rule #	Situation	Outcome (event or censored)	Date of event or censoring
1	Patient died due to respiratory cause and the date of the event is known	Event	Date of event
2	Patient died due to respiratory cause and the date of the event is unknown	Event	Imputed date of event
3	Patient is alive	Censored	Date of last contact when the patient was known to be alive
4	Patient status is unknown	Censored	Date of last contact when the patient was known to be alive and event free

5.3.2.5 Time to progression or death over the whole trial

Progression is defined as the date when $\geq 10\%$ of absolute decline in FVC % pred occurs for the first time. For those patients who progressed or died due to any causes within the trial, time to progression or death due to any cause [days] will be computed as:

- Earliest of date of documented progression event or death – date of first drug intake + 1

Patients who did not experience any event will be censored at the date of last contact when the patient was known to be alive and was known not to have progressed.

Patients who did not experience any event during their trial participation will be censored according to the mechanism for censoring as described in Table 5.3.2.5: 1.

Table 5.3.2.5: 1 Censoring Rules for Time to progression or death over the whole trial

Rule #	Situation	Outcome (event or censored)	Date of event or censoring
1	Patient had a documented progression or died and the date of the event is known	Event	Earliest Date of event
2	Patient had a documented progression or died and the date of the event is unknown	Event	Imputed date of event
3	Patient did not have a documented progression and is alive	Censored	Date of last contact when the patient was known to be alive and event free
4	Patient status is unknown	Censored	Date of last contact when the patient was known to be alive and event free

5.4 OTHER VARIABLES

5.4.1 Demographics and baseline characteristics

5.4.1.1 Demographic data

- Gender
- Ethnicity: overall and by race
- Race: single race respondents, multiple race respondents (all combinations ticked), and all race categories regardless of how many race categories were ticked
- Age [years] at time of informed consent (transferred by IRT)
- Age in categories [years] (<30; ≥ 30 -<45; ≥ 45 and <60; ≥ 60 and <75; ≥ 75)

- Weight [kg] as continuous variable and in classes (<30; ≥ 30 - <60; ≥ 60 - <90; ≥ 90)
- Height [cm]
- Body mass index [kg/m^2]: Weight[kg] / Height [m]*Height[m], as a continuous variable and in classes (< 18.5; ≥ 18.5 -<25; ≥ 25 -<30, ≥ 30)
- Tobacco consumption (Never, Current, Former)
- Pack years (for patients who tick “*Current*” or “*Former*” in the variable “Tobacco consumption”) as continuous variable and in classes (< 20; ≥ 20 -<40; ≥ 40)

5.4.1.2 Trial indication

- Time elapsed since the first diagnosis of ILD [years] will be calculated as: (date of randomisation – date of first diagnosis of ILD) / 365.25
- Time elapsed since the first diagnosis of ILD will also be coded in classes (≤ 1 year; > 1 year to ≤ 3 years; > 3 years to ≤ 5 years; > 5 years)
- Underlying ILD diagnosis (“*Idiopathic nonspecific interstitial pneumonia*”, “*Unclassifiable idiopathic interstitial pneumonia*”, “*Hypersensitivity pneumonitis*”, “*Rheumatoid Arthritis associated ILD*”, “*Mixed connective tissue disease*”, “*Systemic sclerosis associated ILD*”, “*Exposure-related ILD*”, “*Sarcoidosis*”, “*Other fibrosing ILD*”)
- Underlying ILD diagnosis in groups
 - *Hypersensitivity pneumonitis (HP)*
 - *Idiopathic nonspecific interstitial pneumonia (iNSIP)*
 - *Unclassifiable idiopathic interstitial pneumonia (uIIP)*
 - *Autoimmune ILDs (auto)*
 - Other ILDs (other)
- Autoimmune ILD (Sub-classification based on the underlying ILD diagnosis categories “*Rheumatoid Arthritis associated ILD*”, “*Mixed connective tissue disease*” and “*Systemic sclerosis associated ILD*” and the classification of “*Other fibrosing ILDs*” shown in [Table 9.13: 1](#) with the flag “*autoimmune ILD*”)
- Exposure-related ILD (Sub classification based on the underlying ILD diagnosis category “*Exposure related ILD*” and the classification of “*Other fibrosing ILDs*” shown in [Table 9.13: 1](#) with the flag “*exposure related ILD*”)
- Other ILDs (Sub-classification based on the underlying ILD diagnosis category “*Sarcoidosis*”, exposure-related ILDs and the classification of “*Other fibrosing ILDs*” shown in [Table 9.13: 1](#) with the flag “*other ILD*”)
- ILD history including:
 - Time since ILD diagnosis based on imaging [years]
 - Diagnosis of ILD confirmed by surgical biopsy (Yes, No, Unknown)
 - Diagnosis of ILD confirmed by transbronchial biopsy (Yes, No, Unknown)
 - For auto-immune ILD (only): Time since rheumatologic diagnosis [years]

- For auto-immune ILD (only): Diagnosis confirmed by a rheumatologist? (Yes, No, Unknown)
- For exposure related ILDs (only): exposure still present (Yes, No)
- Criteria for progressive ILD (all combinations of: Decline in FVC % pred $\geq 10\%$, Decline in FVC % pred $\geq 5-10\%$ combined with worsening of respiratory symptoms, Decline in FVC % pred $\geq 5-10\%$ combined with increasing extent of fibrotic changes on chest imaging, Worsening of respiratory symptoms as well as increasing extent of fibrotic changes on chest imaging)
- HRCT assessment results:
 - HRCT pattern (“HRCT with UIP-like fibrotic pattern only”, “Other HRCT fibrotic patterns”)

5.4.1.3 Baseline characteristics for lung function

- FVC [ml]
- FVC [% predicted]
- FEV1 / FVC
- Oxygen Saturation on Pulse Oximetry (SpO2) [%]
- DLCO (corrected for Hb) [% predicted]: refer to [Section 5.3.1.4](#) for the derivation of DLCO % pred.

5.4.1.4 Baseline characteristics for questionnaires and derived outcomes

- K-BILD breathlessness and activities score, psychological score, chest symptoms score, and total score
- L-PF
 - Total score
 - Impact score
 - Symptoms dyspnea, cough, and fatigue domain scores and total score
- PF-IQOL summary score

5.4.2 Compliance

5.4.2.1 Over 52 weeks

Compliance will be calculated over 52 weeks as:

$$\text{Compliance [%]} = \frac{\text{Number of capsules actually taken over the 52 - week treatment period}}{\text{Number of capsules which should have been taken over the 52 - week treatment period}} \times 100$$

The number of capsules which should have been taken over the 52-week treatment period will be calculated as:

Number of capsules which should have been taken over the 52-week treatment period
[capsules] = (date of last administration^[1] – date of first administration + 1) [days] × 2^[2]

[1] Or Visit 9, if earlier.

[2] The time of first/ last administration are taken into account, so only one capsule may be expected to be taken on some days (calculation is then adapted accordingly).

In case of dose reduction to 100 mg bid, the number of capsules taken per day is still 2, so the calculation of compliance remains the same. Only treatment interruptions not due to AE will be considered as a compliance issue and will be taken into account in the calculation (duration of interruptions due to AE will be subtracted from the duration of the treatment period, as defined in [Section 6.1](#)).

Compliance will also be categorised into classes: <50%, ≥50% - <80%, ≥80% - ≤ 120%, > 120%.

5.4.2.2 Over the whole trial

Similarly, compliance over the whole trial will be calculated and categorised into the same classes.

5.4.3 Exposure

5.4.3.1 Over 52 weeks

Duration of exposure [months] = (date of last administration^[1] – date of first administration +1 day) / 30.5

[1] Or week 52 time-point (372 days after date of first trial drug intake), if earlier.

Duration of exposure in categories: ≤3 months (91 days); >3 months (91 days) to ≤ 6 months (182 days); > 6 months (182 days) to ≤12 months (365 days); > 12 months (365 days)

Treatment interruptions will not be subtracted from the duration of exposure.

Duration on actual dose (100 or 150 mg bid) (sum of durations on-treatment for each dose effectively taken): in weeks and in categories (≤ 8 weeks, > 8 weeks)

Total dose [g]: Duration of exposure [days] * actual dose [g]

Dose intensity [%]: amount of drug actually administered over the study (dose 100mg and 150mg) divided by the amount of drug that would have been administered had dose 150mg bid been administered over all the study (from date of first administration to date of last administration, whether or not trial drug was prematurely discontinued). Dose intensity will be summarized in percent and in categories (≤ 30 %, >30% - ≤50%, >50% - ≤90%, >90% - <100%, 100%).

Time to first dose reduction or time to first treatment interruption in classes : ≤ 31 days, $> 31 - \leq 91$ days, $> 91 - \leq 182$ days, > 182 days

Time to first dose reduction, time to first treatment interruption, as well as time to premature treatment discontinuation will also be evaluated via survival methods. Censoring rules can be found in Table 5.4.3.1: 1, [Table 5.4.3.1: 2](#) and [Table 5.4.3.1: 3](#) respectively.

Duration of exposure in patient years will also be shown per treatment group.

Table 5.4.3.1: 1 Censoring Rules for Time to first dose reduction over 52 weeks

Rule #	Situation	Outcome (event or censored)	Date of event or censoring
1	Patient had a documented first dose reduction within the first 52 weeks or before the treatment was prematurely ^[1] discontinued and the date of the event is known	Event	Date of event
2	Patient had a documented first dose reduction within the first 52 weeks or before the treatment was prematurely ^[1] discontinued and the date of the event is unknown	Event	Imputed date of event
3	Patient did not have a documented first dose reduction within the first 52 weeks or before the treatment was prematurely ^[1] discontinued	Censored	Earliest of Day 373 (372 days after first drug intake) or date of permanent premature ^[1] drug discontinuation

[1] Prematurely: Discontinuation of the treatment before completion of Visit 9.

Table 5.4.3.1: 2 Censoring Rules for Time to first treatment interruption over 52 weeks

Rule #	Situation	Outcome (event or censored)	Date of event or censoring
1	Patient had a documented first treatment interruption within the first 52 weeks or before the treatment was prematurely ^[1] discontinued and the date of the event is known	Event	Date of event
2	Patient had a documented first treatment interruption within the first 52 weeks or before the treatment was prematurely ^[1] discontinued and the date of the event is unknown	Event	Imputed date of event
3	Patient did not have a documented first treatment interruption within the first 52 weeks or before the treatment was prematurely ^[1] discontinued	Censored	Earliest of Day 373 (372 days after first drug intake) or date of permanent premature ^[1] drug discontinuation

[1] Prematurely: Discontinuation of the treatment before completion of Visit 9.

Table 5.4.3.1: 3 Censoring Rules for Time to premature treatment discontinuation over 52 weeks

Rule #	Situation	Outcome (event or censored)	Date of event or censoring
1	Patient had a documented premature treatment discontinuation within the first 52 weeks and the date of the event is known	Event	Date of event
2	Patient had a documented premature treatment discontinuation within the first 52 weeks and the date of the event is unknown	Event	Imputed date of event
3	Patient did not have a premature treatment discontinuation within the first 52 weeks	Censored	Day 373 (372 days after first drug intake)

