Methodology:	
Placebo controlled, randomized, double-blind, parallel design trial comparing 150 mg nintedanib bid to placebo over a 52 week treatment period (Part A). Patients will continue on blinded randomized treatment (i.e. nintedanib or placebo) until the end of the trial (Part B).
 
The primary assessment of benefit- risk of nintedanib in PF-ILD will be based on the efficacy and safety data over 52 weeks. Additional data beyond the 52 week treatment period will provide supportive longer term information on secondary time to event efficacy endpoints and on safety.
		

Name of company:	Boehringer Ingelheim		
Name of finished product:	Nintedanib		
Name of active ingredient:	Nintedanib		
Protocol date: 13 Sep 2016	Trial number: 1199.247		Revision date: 08 Jun 2018
Methodology continued:	The study population will be enriched for patients with PF-ILD with Usual Interstitial Pneumonia (UIP) pattern. UIP pattern will be defined based on High Resolution Computed Tomography (HRCT) using the same HRCT criteria as in the Phase III IPF trials with nintedanib. Since these criteria differ slightly from the current definition of radiologic UIP provided in the American Thoracic Society/European Respiratory Society (ATS/ERS) guidelines, screening HRCT meeting the protocol criteria for UIP as confirmed by central review will be referred to as "HRCT with UIP-like fibrotic pattern only"		
No. of patients:			
total entered:	600		
each treatment:	Nintedanib: 300 Placebo: 300		
Diagnosis :	Physician diagnosis of PF-ILD		
Main criteria for inclusion:	Patients aged \geq 18 years with PF-ILD, defined as patients who present with features of diffuse fibrosing lung disease of $>10\%$ extent on HRCT and whose lung function and respiratory symptoms or chest imaging have worsened despite treatment with unapproved medications used in clinical practice to treat ILD.		
Test product(s):	Nintedanib		
dose:	150 mg bid (300 mg daily) with optional dose reduction to 100 mg bid (200 mg daily) to manage adverse events		
mode of administration:	Per os		

Name of company:		Boehringer Ingelheim	
Name of finished product:		Nintedanib	
Name of active ingredient:		Nintedanib	
Protocol date: 13 Sep 2016	Trial number: 1199.247		Revision date: 08 Jun 2018
Comparator products:	Placebo matching nintedanib soft gelatine capsules		
dose:	N/A		
mode of administration:	Per os		

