4.1.4 Drug assignment and administration of doses for each patient

The treatment for an individual patient will be assigned by means of an IRT contact during Visits 2, 4, 6, 7, 8, 9 to X. Patient will receive either active drug at a dosage of 150 mg bid or placebo bid.

Trial medication will consist of 1 capsule twice daily (bid) administered orally throughout the study. Wallets covering 4 weeks + 1 week reserve treatment will be dispensed to the patient:

- 1 wallet at Day 1 (randomization = Visit 2) (30 days plus 5 days reserve)
- 2 wallets at Visit 4 (60 days plus 10 days reserve)
- 3 wallets at Visit 6 and Visit 7 (90 days plus 15 days reserve)
- 4 wallets at Visit 8 (120 days plus 20 days reserve)
- 4 wallets at Visit 9 (120 days plus 20 days reserve)
- 4 wallets at Visit X (120 days plus 20 days reserve)

Trial medication will be administered orally on a twice daily basis (bid). The patients should swallow the trial medication, without chewing, together with a glass of water (~250 mL), and should observe a dose interval of 12 hours. Trial medication needs to be taken at the same time every day (between 06:00 and 11:00 in the morning, and between 18:00 and 23:00 in the evening). Because nintedanib may cause stomach discomfort, it is recommended to take the trial medication after food intake.

A forgotten dose should be skipped if the time window to the next dose is less than 8 hours. The following dose should be taken according to the protocol. No catch up of missed doses is permitted.

The investigational product should only be dispensed to participating patients according to the protocol by authorized personnel as documented in the form “Investigator’s Trial Staff”.

In case of adverse events requiring dose reduction between planned visits, an additional site visit is required. 100 mg bid (or matching placebo) will be assigned by means of an IRT call from the Investigator (see [Section 6.2.4](#)). The colour of capsules (100 mg capsule or corresponding placebo) will be slightly different but the packaging will remain the same (same number of capsules per blister and same number of blisters per wallet).

The dose can be reduced without prior interruption, i.e., immediately stepping down from 150 mg bid to 100 mg bid if necessary due to adverse events which require a special trial visit according to procedures described in [Section 4.2.1](#).

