4.2 CONCOMITANT THERAPY, RESTRICTIONS, AND RESCUE TREATMENT

4.2.1 Rescue medication, emergency procedures, and additional treatment(s)

Rescue medication to reverse the action of nintedanib is not available.

Dose reduction from 150 mg bid to 100 mg bid or treatment interruption should be considered to manage adverse events. No further dose reduction is possible for patients on the 100 mg bid regimen. In case of persistent adverse events observed at this dose, or severe effects at 150 mg bid, permanent treatment discontinuation should be considered.

Treatment interruption, reduction and re-increase are allowed at multiple occasions.

Table 4.2.1: 1 Allowed treatment reduction / interruption periods:

	AEs considered related to study drug	AEs not considered related to study drug
Maximum interruption	4 weeks	8 weeks
Recommended restart	with reduced dose (100 mg bid)	with the same dose as before interruption (100 mg bid or 150 mg bid)
Re-escalation	within 4 weeks to 150 mg bid	N/A

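### The total-dose formula in SAP 5.4.3.1 counts interruption days as dosed days and leaves the dose term undefined, so it overstates drug taken for patients who interrupt treatment

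*SAP*

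**What the plan says.** SAP 5.4.3.1 defines duration of exposure as last administration minus first administration plus one day. For the 52-week analysis the end is capped: "Or week 52 time-point (372 days after date of first trial drug intake), if earlier". It then adds "Treatment interruptions will not be subtracted from the duration of exposure".

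Three further measures follow:

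- Time at each dose level: "Duration on actual dose (100 or 150 mg bid) (sum of durations on-treatment for each dose effectively taken").
- Cumulative drug: "Total dose [g]: Duration of exposure [days] * actual dose [g"].
- Dose intensity, whose numerator is the "amount of drug actually administered over the study (dose 100mg and 150mg"). Its denominator is what 150 mg bid throughout would have given between first and last administration.

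SAP 5.4.3.2 carries all of these, total dose included, over to the whole trial.

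The protocol synopsis gives the daily amounts: "150 mg bid (300 mg daily) with optional dose reduction to 100 mg bid (200 mg daily"). Protocol 4.2.1 states that "Treatment interruption, reduction and re-increase are allowed at multiple occasions". Its Table 4.2.1: 1 limits an interruption to 4 weeks for related adverse events and 8 weeks for unrelated ones.

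**The concern.** The total-dose formula uses duration of exposure, which the plan has just said keeps interruptions in. The measure that leaves them out, on-treatment time at each dose level, stands between the two lines but is not used. Applied as written, the formula gives a patient who stopped for four weeks the same cumulative dose as one who never stopped.

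Two further gaps leave room for different programs:

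- The dose carries the unit g, with no indication that it is per day.
- A patient who steps down to 100 mg bid and later returns to 150 mg bid has no single dose to put into the product.

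Interruption followed by dose reduction and re-escalation is part of the planned handling of adverse events, so this will arise in ordinary use. At stake is a safety-exposure figure that would be wrong for interrupted patients and would not agree with dose intensity reported beside it.

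**Working it through.** The documents state no numerical total dose, so there is no figure of the plan's own to reproduce. The daily amounts in the synopsis do check: 2 × 150 = 300 mg and 2 × 100 = 200 mg.

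**Inputs**

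- Longest countable duration over 52 weeks: 372 + 1 = 373 days (SAP 5.4.3.1).
- Daily amount: 0.3 g at 150 mg bid and 0.2 g at 100 mg bid (protocol synopsis).
- Longest single interruption: 28 or 56 days (Protocol Table 4.2.1: 1).

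**Formulas**

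- As written: 373 × daily amount, whatever the interruptions.
- Drug taken: sum over dose levels of on-treatment days × daily amount.

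**One dose level, 150 mg bid**

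| Days off | As written (g) | Drug taken (g) | Error | Dose intensity |
|---|---|---|---|---|
| 0 | 373 × 0.3 = 111.9 | 373 × 0.3 = 111.9 | 0.0% | 100.0% |
| 28 | 111.9 | 345 × 0.3 = 103.5 | 111.9/103.5 − 1 = +8.1% | 345/373 = 92.5% |
| 56 | 111.9 | 317 × 0.3 = 95.1 | 111.9/95.1 − 1 = +17.7% | 317/373 = 85.0% |

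The last column shows the inconsistency. Dose intensity falls from 100% to 85.0% while total dose stays at 111.9 g.

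**Two dose levels (an assumed course, for illustration)**

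Take 100 days at 150 mg bid, 28 days off, 28 days at 100 mg bid and 217 days at 150 mg bid, which is 373 days in all.

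- Drug taken: 100 × 0.3 + 28 × 0.2 + 217 × 0.3 = 30.0 + 5.6 + 65.1 = 100.7 g.
- Higher level throughout: 373 × 0.3 = 111.9 g, an error of +11.1%.
- Lower level throughout: 373 × 0.2 = 74.6 g, an error of −25.9%.

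For a patient with both levels, even the direction of the error depends on a choice that the formula leaves open.

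**The case against.** **Twice-daily dosing.** A reader might infer that the formula ignores it, since no factor of 2 appears. The documents do not support that. The line just above the formula ties actual dose to 100 or 150 mg bid, and the synopsis equates 150 mg bid with 300 mg daily. What is missing is the words per day. The stronger reading would also reverse the direction of the error: at 0.15 g the formula gives 373 × 0.15 = 55.95 g, half of 111.9 g. It is therefore an alternative to the overstatement and cannot be added to it.

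**Per-dose derivation is already planned.** SAP 5.4.3.1 sums on-treatment time for each dose, SAP 6.1 defines an off-treatment period for interruptions, and SAP 7.7.1 reports duration and dose intensity by dose strength. A careful programmer may well do the right thing. This stands as evidence that the data exist. It does not change a formula that names a different duration.

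**Different measures may differ.** Grams and a percentage need not coincide. But both claim to describe drug received, and the numerator of one is the natural value of the other.

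**Active arm.** A reader might infer a sizeable bias against or for nintedanib. Protocol 1.2 reports diarrhoea in 62.4% on nintedanib and 18.4% on placebo in the IPF trials, and says that the common events were managed partly by interruption or reduction. More error in the active arm is therefore plausible. The documents give no interruption rate or mean length, so no group effect can be calculated. The 56-day limit applies to unrelated events (and, in Protocol 4.2.1.3, to exacerbations), so the 17.7% says nothing about drug-related interruptions.

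**Consequence.** Exposure is descriptive. SAP 7.7 to 7.7.2 do not name total dose among the outputs, interruptions are summarised separately, and the adverse event rates in SAP 7.8.1.5 use time at risk. This stands and limits the weight of the point.

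**Conclusion.** The definition is wrong as written for any patient with an interruption. With the dose taken as the daily amount, total dose over a 373-day course at 150 mg bid is overstated by 8.1% for 28 days off and by 17.7% for 56 days off. Without an interruption or a dose change there is no error. The dose term also needs its unit (per day) and a rule for patients who have taken both levels.

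The percentages are for single patients at the longest permitted single interruption, at one dose level, counting every on-treatment day as two capsules. Shorter interruptions give less. Repeated ones, which the protocol allows, can give more, and over the whole trial they can accumulate.

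The effect is confined to a descriptive exposure summary. The primary FVC analysis, the type I error, the power and the adverse event rates do not depend on it.

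**What to change.** Replace the total-dose line in SAP 5.4.3.1 with: total dose [g] is the sum, over the two dose levels, of on-treatment days at that level (interruption days excluded) times the daily amount at that level, namely 0.3 g per day for 150 mg bid and 0.2 g per day for 100 mg bid. State that this quantity is also the numerator of dose intensity, so that both come from one derived variable. SAP 5.4.3.2 then follows by its existing reference.

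Duration of exposure can keep its definition, interruptions included, as a measure of calendar time.

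The cost is one line of the SAP. On-treatment time by dose level and the amount administered are already planned for other outputs in the same section, so no new data are needed.
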